## **10 MONITORING**

### **10.1 Data and Safety Monitoring Plan**

At each follow-up visit, study staff will query participants about each of the following: review previously reported medications and current use of previously reported medications; any new medications; any side effects from the melatonin; any unexpected medical conditions since their last visit; any new medical diagnoses or changes in medical history since their last visit. Side effects and adverse events will be reviewed with the participant by the study clinician at each follow-up visit. The PI will have oversight of the medical history data, medications, and side effect data for each participant. Only changes to medications/medical history/side effects which occur after the first treatment session/treatment initiation will be recorded. Changes to medications/medical history/side effects deemed by the PI to be possibly, probably, and definitely related to melatonin use will be reported as adverse events.

The PI will be primarily responsible for monitoring data integrity. Monitoring is intended to protect participants' rights and safety, and to ensure the integrity and quality of the data collected. The PI will ensure that all relevant IRBMED and FDA policies, procedures, and stipulations are followed by the study team.

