### **6.2 Treatment Study Period**

#### **Visit 1 (Day 1)**

Participants will have their first session with the study clinician at Visit 1. Prior to the session, study staff will meet with the participant to download their actigraphy. Study staff will provide the study clinician with the initial clock time at which each participant should take melatonin. The initial clock time of melatonin administration for participants assigned to the M-DLMO condition will be set at 3 h before their measured baseline DLMO. The initial clock time of melatonin administration for participants assigned to the E-DLMO condition will be set at 5 h before their average time of sleep onset at baseline per most recent 7 days of actigraphy. Participants be provided with a 14-day supply of melatonin 0.5 mgs, which they will begin taking that evening.

During the first visit, study staff will query whether participants have had any changes in their medications or medical history since the screening, and review concomitant medications. Participants' baseline sleep diary and actigraphy data will be reviewed by the study clinician. The study clinician will provide them with specific instructions regarding when to take melatonin, their bed time, their wake time, and when to dim ambient lighting and electronic devices to their lowest usable level (timed to be approximately 60 minutes before their scheduled bedtime). They will be provided with a handout summarizing this information.

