## 7 ASSESSMENTS

**Table 1. Protocol Activity by Visit**

Protocol Activity	Screen/ Baseline	Visit 1	Follow-up 1	Follow-up 2	Follow-up 3	Follow-up 4 (Final)
		Day 1	Day 7 $\pm$ 5 business days	Day 14 $\pm$ 5 business days	Day 21 $\pm$ 5 business days	Day 28 $\pm$ 5 business days
Week (approximate)	0	1	2	3	4	5
Visit #	0	1	2	3	4	5
Informed Consent	X					
Interview and Medical History	X					
Pregnancy Test (females of childbearing potential)	X					
Randomization	X					
DLMO	X					X
Daily sleep diary	X	X	X	X	X	X
Wrist actigraphy	X	X	X	X	X	X

Melatonin Treatment		X	X	X	X	X
Adverse Event Assessment			X	X	X	X
Concomitant Medication Assessment	X	X	X	X	X	X
Daytime functioning and sleep self-report measures	X					X

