## 7.1 Primary Endpoint Assessments

Protocol activity and assessments are summarized in Table 1 above.

Primary endpoint: change in the time of DLMO from pre- to post-treatment.

To assess time of DLMO, all eligible participants (regardless of group assignment) will undergo in-home salivary DLMO collection at pre- and post-treatment, using the protocol established by [name] (Co-I) ([name] et al. 2015). Participants will be oriented to the collection procedures during their clinic visit. Participants will be in dim light starting 30 minutes prior to the first sample collection. Collection begins 6 hours prior to participants' habitual sleep onset per their most recent week of actigraphy at baseline. At post-treatment, collection begins 6 hours prior to participants' bed time as assigned at the final treatment session. Samples are collected via Salivette every 30 minutes until bedtime (13 samples total). They are provided with a kit, which includes: a checklist of procedures; a test tube rack; a toothbrush; a nightlight; blue-blocking Uvex glasses (with an Actiwatch attached to monitor compliance of use); an iPod programmed to alarm at collection times; a light medallion (an Actiwatch with light sensor worn around the neck to monitor compliance with light exposure); Salivette collection vials equipped with Track Cap, which will record when the vial was opened; and a label dispenser with pre-labeled labels. Participants wear the blue-blocking glasses throughout the dim light saliva collection and are required to remain seated in the 10 minutes before each sample. When the iPod alarms, participants brush their teeth without toothpaste, collect saliva by chewing on the Salivette, and deposit it in the vial. Participants are informed about the compliance measures utilized in the study. Samples will be stored in participants' freezers until they can be transported to our facility. Samples are centrifuged for two minutes, frozen, and assayed using Bühlmann Laboratory radioimmunoassay (ALPCO Diagnostics, Salem, NH) at **Solidphase Inc.** To ensure consistency and to minimize the effects of sleep schedule changes on the weekends/days off of work, whenever possible, all participants will complete DLMO collection on the third night of their typical workday sleep schedule (e.g., DLMO collection will occur on a Wednesday, Thursday, or Friday night for participants who work a traditional Monday-Friday schedule).

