*Unexpected adverse events are those that are not anticipated in the study informed consent. This includes adverse events for which the specificity or severity is not consistent with the description in the informed consent.*

*Unanticipated problem: Per FDA Procedural Guidance for Clinical Investigators, Sponsors, and IRBs (January 2009), A serious problem that has implications for the conduct of the study (requiring a significant and usually safety-related, change in the protocol such as revising inclusion/exclusion criteria or including a new monitoring requirement, informed consent or investigator's brochure).*

*Unanticipated problem Reporting: Per 21 CFR 312.66, 312.53 (c)(1)(vii), and 56.108(b)(1), should an Unanticipated problem occur during the investigation, the investigator will promptly report all unanticipated problems involving risks to human subjects or others to IRBMED /FDA.*

*The severity or grade of an adverse event may be measured using the following definitions:*

**Mild:** Noticeable to the subject, but does not interfere with subject's expected daily activities, usually does not require additional therapy or intervention, dose reduction, or discontinuation of the study.

**Moderate:** Interferes with the subject's expected daily activities, may require some additional therapy or intervention but does not require discontinuation of the study.

**Severe:** Extremely limits the subject's daily activities and may require discontinuation of study therapy, and/or additional treatment or intervention to resolve.

**Event reporting:** Information regarding potential adverse events (AE) will be collected by participant report at each study assessment/follow-up. [name] will ensure that all protocol deviations, AEs, and SAEs are reported to the IRB and FDA according to the applicable regulatory requirements. AEs will be reported according to the study-specific reporting timeline outlined below. Only related adverse events will be reported.

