### **Potential Risks of the Study:**

- 1 Risk: Breach of confidentiality  
Likelihood of risk: Rare  
Seriousness to the subject: Minimal
2. Risk: Saliva collection. There is a risk of choking on salivette chewing swab.  
Likelihood of risk: Rare  
Seriousness to the subject: Serious
3. Risk: Actigraphy. Minimal risks exist with actigraphy. It is possible that participants may experience some discomfort from the band.  
Likelihood of risk: Infrequent  
Seriousness to the subject: Minimal
4. Risk: Clinical interview and questionnaires. Participants may feel psychological discomfort when being interviewed or completing questionnaires related to their insomnia, mood, or health.  
Likelihood of risk: Rare  
Seriousness to the subject: Minimal
5. Risk: Melatonin side effects. The safety of melatonin has been well-documented in both animal and human studies, with no studies showing evidence of serious adverse events from melatonin. Possible side effects include drowsiness, headache, dizziness, or nausea.  
Likelihood of risk: Infrequent  
Seriousness: Minimal

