**Table 2. Study-Specific AE Reporting Timeline**

Reportable Events	Timing of Report to IRB and FDA
Unanticipated problem involving risks to subjects or others related to this research study	Serious: within 7 days Non-serious: with scheduled continuing review
Any physical, social, or psychological harm attributable to participation in this research study (e.g., an injury occurring during a study visit, infection at the site of a blood draw if antibiotics are required)	Serious: within 7 days Non-serious: with scheduled continuing review
Death while on study regardless of relatedness	Within 7 days
Privacy violation or breach of confidentiality	Within 7 days
Protocol deviations not related to an adverse event	With scheduled continuing review
Unanticipated problem related to the research that is not a serious adverse event	With scheduled continuing review
Expected, minor side effects commonly associated with melatonin use: 

• Dizziness

• Sleepiness

• Headache

• Nausea

• Transient depression

• Insomnia

• Nightmares or vivid dreams

• Diarrhea

• Irritability

	With scheduled continuing review
Other serious events not attributable to the research except death as noted above	With scheduled continuing review

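### Section 10.1 starts safety recording after the baseline saliva collection and counts only melatonin-related events, and no adverse-event query appears to follow the post-treatment collection

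*Combined protocol and SAP*

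**What the plan says.** Section 10.1 sets when recording starts and which events count. On the start: "Only changes to medications/medical history/side effects which occur after the first treatment session/treatment initiation will be recorded". On content, it says that changes "deemed by the PI to be possibly, probably, and definitely related to melatonin use will be reported as adverse events". Study procedures are not mentioned there.

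In Table 1 the row "Adverse Event Assessment" is marked at Follow-ups 1, 2, 3 and 4. It is blank at Screen/Baseline and at Visit 1, and no column comes after Follow-up 4.

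Other parts of the protocol are wider. Section 8 defines an adverse event as any untoward occurrence in a participant, whatever its cause, and states: "Information regarding potential adverse events (AE) will be collected by participant report at each study assessment/follow-up". Table 2 makes reportable "Any physical, social, or psychological harm attributable to participation in this research study", within 7 days if serious and otherwise at continuing review, with no start date and no link to melatonin. Section 10.2 has staff tell the PI promptly about unexpected events that may be related.

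On the hazard, the list of potential risks in section 8 states: "There is a risk of choking on salivette chewing swab". It rates this risk rare in likelihood but serious for the subject. The other four listed risks are rated minimal.

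On timing, the first melatonin time in the M-DLMO arm "will be set at 3 h before their measured baseline DLMO" (section 6.2, Visit 1). For the second collection, section 7.1 says: "At post-treatment, collection begins 6 hours prior to participants' bed time as assigned at the final treatment session".

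**The concern.** The listed hazard with the worst seriousness rating comes from the swab, and swabs are used only in the two home collections. One collection ends before recording begins. The other seems to take place after the last visit at which anyone is scheduled to ask about adverse events. The relatedness filter in 10.1 adds to this: a swab injury is not related to melatonin, so it could go unlogged as an adverse event even during the recording period. Section 8 also describes a serious adverse event as an adverse drug experience, which leaves the status of a procedural injury unclear.

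At stake is the safety record. A low count of saliva-related events would be hard to interpret if participants were not asked about them at the relevant time. Staff also cannot follow 10.1 to the letter and satisfy section 8 and Table 2 as well. The safety stopping rule in 12.4.1 depends on serious adverse events possibly related to the intervention, so what gets recorded and classified matters there too.

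**Working it through.** The plan gives no figure for this point. The check sets the timing and reporting rules side by side, followed by two short counts.

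1. **Baseline collection against the start of recording.** The M-DLMO starting time is computed from the baseline DLMO and handed to the clinician at Visit 1. Section 7.1 has every eligible participant collect before treatment, whichever arm they are in. The baseline collection therefore precedes Visit 1, and 10.1 records only what happens after that session. Staff do ask at Visit 1 about medical-history changes since screening, but under 10.1 an event that came up there would not be recorded. Result: outside 10.1 recording.

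2. **Post-treatment collection against the start of recording.** It comes after treatment has begun, and 10.1 limits only the start. Result: inside the recording period.

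3. **Post-treatment collection against the last scheduled query.** Table 1 marks DLMO and adverse-event assessment in the same Follow-up 4 column, so the table does not settle the order. Section 7.1 times the collection from a bedtime assigned at the final session, has it done at home, and prefers the third night of the workday schedule. The natural reading is a night after Follow-up 4. Result: probably no scheduled query afterwards. This order is inferred, not stated.

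4. **Content filter.** Section 10.1 reports events related to melatonin. Section 8 defines events regardless of cause, and Table 2 covers harm from participation in general. These three scopes differ.

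5. **Exposure count.** Sampling every 30 minutes over 6 hours gives 6 × 2 + 1 = 13 samples, which matches the figure in section 7.1. Per collection round: 13 × 50 participants = 650 swab uses. Over both rounds: 650 × 2 = 1,300. So 650 precede recording, and 650 fall inside the recording period but, on the reading in step 3, after the last scheduled query. This assumes that all 50 participants complete both collections. It counts exposures and does not estimate events.

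6. **Last dosing days.** Table 1 allows Follow-up 4 at Day 28 ± 5 business days. Five business days span 7 calendar days, so the earliest date is about Day 28 − 7 = Day 21. If tablets still run to Day 28, Days 22 to 28 have no later scheduled query: 7 of 28 days, or 7/28 = 25%. If Follow-up 4 is on Day 28 or later, the figure is 0. The range is 0 to about 7 days, and the upper end is the extreme edge of the visit window.

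**The case against.** A reader might infer that recording closes at Follow-up 4, that both collections fall outside it, and that the trial would therefore report no saliva-related events. The documents do not support this. No section gives a closing date. The sentence in 10.1 restricts only the start, so the post-treatment collection lies within it. Table 2 makes serious harm from participation reportable within 7 days whenever it occurs, and section 10.2 has no time limits. A serious choking event that becomes known is therefore reportable under the plan.

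It can also be argued that 10.1 is in effect a log of melatonin side effects, which naturally starts with treatment, while Table 2 is a separate route for harm from participation. That reading is reasonable, but the protocol does not state it. The sentence in 10.1 also covers medications and medical history, so it is not confined to side effects. Table 1 does schedule a concomitant-medication check at Screen/Baseline and Visit 1, but that is not an adverse-event enquiry.

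It is further fair to say that the choking risk is rated rare, that saliva-sampling safety is neither an objective nor an endpoint, and that both arms undergo the same collections. All of this stands, and it limits the consequence to safety capture. What it does not answer is that Table 2 and section 10.2 work only once someone knows of the event. Non-serious swab events are the ones least likely to be volunteered.

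**Conclusion.** The point holds as a gap in active capture and recording, and as an inconsistency between sections. Harm at the baseline collection is excluded from recording by a stated rule, and this needs no inference. For the post-treatment collection the finding is narrower: it is inside the recording period, but no query is scheduled after it if, as section 7.1 suggests, it follows Follow-up 4. No end of adverse-event collection is defined. The melatonin-only filter in 10.1 conflicts with the wider scopes in section 8 and Table 2.

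In size, this concerns 650 planned swab uses before recording and 650 more without a later scheduled query, assuming full completion. Up to about 7 dosing days are also affected if Follow-up 4 is held as early as allowed and dosing continues to Day 28. Neither figure is an expected number of missed events. A reader might take the 25% as a typical loss of drug-safety follow-up, but it is the worst case of the visit window.

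The gap mainly affects non-serious or unvolunteered events. It does not bias the primary comparison of DLMO change. The plan should be changed, because the gap involves its only risk rated serious and closing it is cheap.

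**What to change.** - **Section 10.1:** start recording at consent or at the first study procedure. Include procedure-related as well as melatonin-related events. Label events before the first tablet as pre-treatment, so that treatment-emergent counts stay clean.
- **Table 1:** mark the adverse-event row at Screen/Baseline and Visit 1.
- **End of collection:** add one adverse-event query when the post-treatment saliva samples are returned, covering the collection night and any tablets taken since Follow-up 4. State that this query ends adverse-event collection.
- **Consistency:** align sections 8 and 10.1 and Tables 1 and 2 on start, end and procedure-related events.

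The cost is revised wording in 10.1 with matching edits elsewhere, two marks in Table 1, and a question at contacts the study already needs: Visit 1 and the hand-over of the frozen samples. The downside is a few more minor events to log.

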### **10.2 Frequency of Data and Safety Monitoring**

Study staff will inform the PI of potentially related unexpected events as soon as they occur. The PI will be informed of related serious adverse events as soon as they occur and will notify the IRB and FDA within 7 days of notification.

## **11 DATA HANDLING AND RECORD KEEPING**

### **11.1 CRFs / Electronic Data Record**

All data, including Case Report Forms, will be collected and maintained in REDCap.

### **11.2 Record Retention**

Per 21 CRF §312.62, study records will be retained for 2 years after the investigation is discontinued.

## **12 ETHICS**

### **12.1 IRB/FDA**

Prior to study commencement, an Investigator Initiated Investigational New Drug (IND) will be submitted to the Food and Drug Administration (FDA), for review and approval. The study will also be reviewed and approved by the Institutional Review Board (IRBMED, University of Michigan, Ann Arbor, MI).

This study will be carried out in compliance with the protocol and the principles of good clinical practice, as described below:

### **12.2 Institutional Review Board (IRB)**

Before implementing this study, the protocol, the proposed informed consent form and other information to be provided to subjects, must be reviewed by a properly constituted Institutional Review Board (IRB). Any amendments to the protocol must be reviewed and approved by IRBMED.

### **12.3 Subject Information and Consent**

The study team member will explain to each subject (or legally authorized representative) the nature of the study, its purpose, the procedures involved, the expected duration, the potential risks and benefits involved and any discomfort it may entail. Each subject will be informed that participation in the study is voluntary and that he/she may withdraw from the study at any time and that withdrawal of consent will not affect his/her subsequent medical treatment or relationship with the treating physician.

This informed consent will be given by means of a standard written statement, written in non-technical language. The subject should read and consider the statement before signing and dating it, and should be given a copy of the signed document. If the subject cannot read or sign the documents, oral presentation may be made or signature given by the subject's legally appointed representative, if witnessed by a person not involved in the study, mentioning that the patient could not read or sign the documents. No patient can enter the study before his/her informed consent has been obtained.

The informed consent form is considered to be part of the protocol, and will be submitted for IRB approval.

### **12.4 STUDY DISCONTINUATION CRITERIA**

#### ***12.4.1 Stopping Rules for Safety reasons***

The trial will be stopped if any serious adverse events occur that could possibly be related to the intervention.

#### ***12.4.2 Rules for Discontinuation of a Subject***

In the event a patient drops out of the study or is discontinued due to protocol violations, all attempts will be made to exit the patient in accordance with the protocol requirements.

## **14 APPENDIX**

In order to maintain participant and study staff's safety, the following protocol changes may be made during a viral outbreak or pandemic, per clinical judgement and in line with all institutional guidance/requirements with subjects:

1. We will follow all institutional guidance/requirements regarding in person contact with subjects.
2. When appropriate, participants will be provided with all materials necessary so that they may complete their study participation, including intervention sessions, remotely per sponsor allowance for Virtual Clinic Visits per clinician/subject discretion/institutional or government allowance to reduce or eliminate in-person contact with the study team. Specifically, we will provide the participant with enough supplies to complete post treatment in-home saliva collection and a 28-day supply of melatonin.
3. We will continue to screen participants for initial eligibility; all screening will take place remotely and will not involve any in-person interactions with participants. Participants will complete e-consent through REDCap to provide their written consent prior to completion of remote screening.
4. Further screening for participants who meet initial eligibility will be deferred until in-person interactions with participants may be resumed. Participants who passed the initial eligibility screen and completed e-consent will be re-consented in-person at their, in-person second eligibility screen.
5. Screening interviews and intervention sessions may take place via an online video system (i.e., BlueJeans, Zoom Health), or over the phone.
